**(8) Pharmacovigilance**

**AE/SAE/Pregnancy will be collected as below;**

- **Adverse event reporting:** An adverse event is the appearance or worsening of any undesirable sign, symptom, or medical condition occurring after starting the study drug even if the event is not considered to be related to study drug.

- Serious adverse event reporting

An SAE is defined as an event which is fatal or life-threatening or results in persistent or significant disability/incapacity or constitutes a congenital anomaly/birth defect or requires inpatient hospitalization or prolongation of existing hospitalization or medically significant

\* Any other protocol specific SAE criteria or SAE exemption will be described on protocol.

Every SAE, regardless of suspected causality, occurring after the patient signs the informed consent must be reported to Novartis after learning of its occurrence. All SAE form should be reported to local Novartis Safety Desk according to agreed procedure with Novartis within **15 days** of learning by the investigator.

- **Pregnancies:** Pregnancy should be recorded on a Clinical Trial Pregnancy Form and reported by the investigator to the sponsor, and the sponsor should forward that form to the local Novartis Safety Desk according to agreed procedure with Novartis within **15 days** of learning by the investigator.

**(9) Study duration**

**Until 30 Jul 2017(CSR submission)**

## **(10) Methodology**

Primary and secondary endpoints:

Primary endpoint:

To compare other visual acuity, anatomical changes after intravitreal Ranibizumab injection from baseline through 6 months after treatment.

i) The changes in best corrected visual acuity (BCVA) using ETDRS chart. ii) The central macular thickness - Circle Diameters : 1 mm ETDRS by spectralis OCT ; Heidelberg Engineering.

Secondary endpoints:

To compare microaneurysmal changes and perifoveal non-perfusion area and safety after intravitreal Ranibizumab injection from baseline through 6 months after treatment.

i) The total number of microaneurysm by fundus photo using Retmarker DR(version 1.0.2) software.

ii) The microaneurysm formation rate : Number of new MAs detected/month. iii) The microaneurysm disappearance rate : Number of MAs that resolved/month. iv)The microaneurysm turnover. v) Perifoveal non-perfusion area in FAG (mm^2) using ImageJ software (version 1.52a) by FAG image.

vi) Safety parameters : Systemic adverse events (MI, CVA, etc), Ocular adverse events (retinal detachment, RPE tear, endophthalmitis, uveitis, vitreous hemorrhage, subretinal hemorrhage, cataract , IOP elevation, etc).

single center, prospective, interventional, one arm, pilot study

Evaluation Participants will be evaluated with a full ocular examination at each visit (VA measurement, tonometry, slit lamp exam). Fluorescein angiography (FA) will be performed at baseline, at 3 months after baseline and at the last visit(6 months after baseline), and OCT will be performed monthly (baseline and 1, 2, 3, 4, 5, 6 months from baseline).

The MAs and perifoveal non-perfused areas in individual retinas were evaluated at 6 months using fundus photography and FA imaging. The Retmarker (version 1.0.2 by Retmarker Ltd, Coimbra, Portugal) software was used for automatic measurement and analysis of changes in number and extent of MAs on fundus photographs and to calculate the total number and turnover of MAs.

Perifoveal non-perfused area was estimated using the early FA image (from each of the three examinations) in which both the vascular arch and the non-perfused area were clearly visualized. Subsequently, the ImageJ software (version 1.25a 23/04/2018 by ImageJ, USA) was used for scaling each image to 200 µm and for equalizing the contrast and sensitivity of each picture to the maximum possible extent, by auto-adjustment of brightness and contrast. The raw red-green-blue (RGB) images were then converted to 8-bit images, with the threshold set for optimal visualization of the non-perfused area. The same threshold was applied to all images of the same patient.

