**ANNEX 1-FINAL NOVARTIS APPROVED PROTOCOL FOR THE STUDY**

## Investigator Initiated Trial

**(1) Title of study**

Effects of Ranibizumab to delay or regression non-proliferative diabetic retinopathy(NPDR) with DME assessed by microaneurysm changes: A pilot study

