**(5) Objectives**

**Objectives:** To evaluate the effects of intravitreal Ranibizumab injection on microvascular changes in eyes of mild-to-moderate NPDR with DME.

**Primary objective:** To compare microvascular changes assessed by microaneurysm counts in eyes of mild-to-moderate NPDR with DME after intravitreal Ranibizumab injection from baseline through 6 months after treatment.

**Secondary objectives:** To investigate other efficacy endpoints including other microvascular, anatomical, visual acuity change and safety in mild-to-moderate NPDR with DME after intravitreal Ranibizumab injection from baseline through 6 months after treatment.

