Sjølie AK et al reported up-regulation of VEGF occurring microaneurysms causes endothelial cell proliferation and inflammation and effusion reaction, so anti-VEGF is effective in early diabetic retinopathy. But there is less effectiveness in late diabetic retinopathy as it reaches the non-changing point. Also Kohner EM et al reported diabetic retinopathy lesions are reversible and could be delayed in early diabetic retinopathy.

So far, changes of microaneurysms in late diabetic retinopathy is uncertain, and if there would be a finding according to anti-VEGF therapy, we could get a clue of surrogate marker which represents treatment results in diabetic retinopathy.

This study was designed to find the clinical evaluation and reduction rate through fluorescein angiography as microaneurysm examination tools to research NPDR with DME treatment results assessed by microaneurysm counts, timely monitored with anti-VEGF therapy.

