### **Statistical Analysis Plan**

Result analysis The investigators compare the differences between at baseline, at 3 month, and at 6 month. Statistical analyses will be performed using SPSS ver.18.0 (SPSS Inc., Chicago, IL, USA). Kolmogorov-Smirnov test was applied to test for normality of sample group data. The repeated measures analysis of variance with Bonferroni correction was used to analyze continuous outcome measures, including BCVA, CRT, total number of MAs, MA formation rate, MA disappearance rate, MA turnover, and perifoveal non-perfused area, before and after completion of 6 months of IVR therapy. A P-value <0.05 was considered statistically significant.

Table 1. Schedule of visits and procedures

Note: X = procedure to be performed, R = rescue treatment	Baseline Month 0 (Visit 1)	Month 1 (Visit 2)	Month 2 (Visit 3)	Month 3 (Visit 4)	Month 4 (Visit 5)	Month 5 (Visit 6)	Month 6 (Visit 7)
Informed consent	X						
Review eligibility criteria	X						
Demographics	X						
ETDRS BCVA	X	X	X	X	X	X	X
Slit lamp exam	X	X	X	X	X	X	X
IOP	X	X	X	X	X	X	X
OCT	X	X	X	X	X	X	X
Color Fundus Photo	X	X	X	X	X	X	X
FA	X			X			X
ICGA	X			X			X
Lucentis® injection	X	X	X	X	X	X	
Adverse events	X	X	X	X	X	X	X

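### Section (10) makes visual acuity and macular thickness the primary endpoint and every microaneurysm measure secondary, the reverse of the primary objective in section (5)

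*Combined protocol and SAP*

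**What the plan says.** All the passages below are current text in Annex 1.

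- **Section (5), primary objective:** "To compare microvascular changes assessed by microaneurysm counts in eyes of mild-to-moderate NPDR with DME after intravitreal Ranibizumab injection". The comparison runs up to month 6.
- **Section (5), secondary objectives:** "To investigate other efficacy endpoints including other microvascular, anatomical, visual acuity change and safety in mild-to-moderate NPDR with DME".
- **Section (10), primary endpoint:** "To compare other visual acuity, anatomical changes after intravitreal Ranibizumab injection from baseline through 6 months after treatment". Two variables follow: change in BCVA on the ETDRS chart, and central macular thickness in the 1 mm ETDRS circle on OCT.
- **Section (10), secondary endpoints:** "To compare microaneurysmal changes and perifoveal non-perfusion area and safety after intravitreal Ranibizumab injection from baseline through 6 months after treatment". Item i is "The total number of microaneurysm by fundus photo using Retmarker DR(version 1.0.2) software"; items ii to iv are MA formation rate, disappearance rate and turnover; item v is perifoveal non-perfusion area; item vi is safety.
- **Section (1), title:** the effect is to be studied "with DME assessed by microaneurysm changes: A pilot study".
- **Section (6), rationale:** the study works "through fluorescein angiography as microaneurysm examination tools to research NPDR with DME treatment results assessed by microaneurysm counts".
- **Statistical Analysis Plan:** "The repeated measures analysis of variance with Bonferroni correction was used to analyze continuous outcome measures, including BCVA, CRT, total number of MAs", followed by the remaining MA measures and non-perfused area, at P<0.05. No outcome is singled out as primary.
- **Section (11):** a Wilcoxon signed rank test for microvascular change, with microaneurysms first in its list. BCVA and thickness are not mentioned.

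**The concern.** The fault is not that BCVA or macular thickness is a poor endpoint. It is that the stated primary endpoint does not measure the stated primary objective. Two analysts could each cite the protocol and report different primary results. If MA count is the primary question, its P-value also depends on whether the analyst follows the Statistical Analysis Plan or section (11).

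The text does not show which order was prespecified. The edition date (18 Jan 2017) is later than the IRB approval (March 2016), parts of section (10) and the Statistical Analysis Plan are in the past tense, and the image-analysis paragraph carries a software date of 23 April 2018. Without a documented history, relabelling either section now could look like a choice made after the results were seen.

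**Working it through.** The plan states no figure that depends on this point. The 25 patients in section (7) come without power, effect size or SD, so there is no calculation to reproduce. The check is a comparison of texts.

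**1. Objectives against endpoints**

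| Measure | Section (5) | Section (10) |
|---|---|---|
| MA count | Primary | Secondary, item i |
| MA formation, disappearance, turnover | Not named; primary or other microvascular | Secondary, items ii to iv |
| BCVA | Secondary | Primary, item i |
| Macular thickness (anatomical) | Secondary | Primary, item ii |
| Non-perfusion area | Not named; fits other microvascular (secondary) | Secondary, item v |
| Safety | Secondary | Secondary, item vi |

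MA count has changed places with BCVA and thickness. Safety is secondary in both sections, and non-perfusion area shows no conflict.

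**2. Counts**

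- Primary variables in section (10): BCVA and thickness = 2, of which MA = 0.
- Secondary items in section (10): i to vi = 6, of which MA = 4 (i to iv).
- Continuous outcomes in the Statistical Analysis Plan: BCVA, CRT, total MAs, formation, disappearance, turnover, non-perfused area = 7, of which MA = 4.

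MA is demoted but still collected and analysed.

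**3. Does another passage settle it?** The title and rationale point to MA. Section (11) names a test only for microvascular change but ranks nothing. The Statistical Analysis Plan lists BCVA and CRT first but sets no hierarchy. Section 19 of the Agreement ranks the Agreement above its Annexes, which does not help because both passages are in Annex 1.

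**4. The wording of the primary endpoint.** The word *other* in its first line has nothing before it to refer to, and it echoes the secondary objectives in section (5). That fits text first written as a secondary endpoint, but does not prove it.

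**5. Dates**

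- IRB approval (1 to 31 March 2016) to edition date (18 Jan 2017): 323 to 293 days.
- Edition date to software date (23 Apr 2018): 460 days.
- Stated study end (30 Jul 2017) to software date: 267 days.

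Some of section (10) therefore seems to have been written after the edition date. This does not show that the endpoint order changed. The software version string is itself unreliable: 1.52a in the endpoint list, 1.25a in the image-analysis paragraph.

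**6. Error rate, for illustration only.** Section (10) gives no success rule for its two primary variables. If success on either were enough, each were tested at 0.05, and the two were independent, the chance of at least one false positive would be 1 − 0.95² = 0.0975, against 0.05 for a single primary MA count. The plan does not say whether its Bonferroni correction covers outcomes or only time points, so this is not a claim about the actual error rate.

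**The case against.** The contradiction between sections (5) and (10) cannot be explained away, but its scope and the remedy can be questioned.

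- **Scope.** Section (5) makes only MA counts primary. Formation rate, disappearance rate and turnover can be read as other microvascular change, so their secondary place need not conflict. This stands: the strict reversal is total MA count against BCVA and thickness, and the count of 4 of 6 describes section (10), not the number of conflicts.
- **Weight of section (11).** It names no primary endpoint and includes non-perfusion area. This stands in part: it shows where the analysis was aimed but does not decide the matter.
- **Default to MA.** If the text does not show what was prespecified, a default may seem to go beyond it. The default rests on the title, the primary objective and the rationale, and it yields to the approved record.
- **Choice of test.** An omnibus ANOVA over three time points does not answer a question about baseline to month 6. That is right, but the Bonferroni-adjusted pairwise contrast or the Wilcoxon test can answer it. What the correction covers must be stated whichever endpoint is primary.
- **Late amendment.** Section 3.9 of the Agreement covers changes before or during the study, and the text may be later than that. Section 20 allows amendment at any time by mutual written consent.
- **Consequence.** This is a one-arm pilot of 25 patients, and the Statistical Analysis Plan gives all seven outcomes one method and one threshold. The harm is therefore to interpretation and prespecification, not to data capture. But the study still declares a primary objective, a primary endpoint and a significance level, and these must agree.

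**Conclusion.** The point holds and must be fixed. Sections (5) and (10) name different primary outcomes, 0 of the 2 primary variables measure what the primary objective asks, and no passage reconciles them. The conclusion rests on the text alone and needs no statistical assumption. The documents do not establish which order was intended, whether the order was ever changed, or whether any change followed sight of the data, and none of these is claimed here.

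**What to change.** 1. **Establish the history.** Take from the IRB-approved version of March 2016 which endpoint was prespecified. Record the date and reason of any change and whether outcome data had been seen.
2. **Make sections (5) and (10) agree.** Unless that record shows otherwise, make change in total MA count from baseline to month 6, by Retmarker on fundus photographs as section (10) defines it, the single primary endpoint. Move BCVA and central macular thickness to secondary, and align the angiography wording in section (6) with that definition. If BCVA and thickness were prespecified as primary, rewrite the objective in section (5) instead and state whether one or both must succeed.
3. **Name one primary test for MA**, the same in the Statistical Analysis Plan and section (11). Either the Wilcoxon signed rank test or the Bonferroni-adjusted pairwise contrast from the repeated-measures ANOVA can serve, if fixed without reference to the results. In either case, say what the Bonferroni correction covers.

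The cost is wording in sections (5) or (10), (6), (11) and the Statistical Analysis Plan, plus a dated change record, handled as a protocol amendment. Under section 3.9 of the Agreement, a change of objectives or procedures that may affect scientific value counts as significant: the funder must be told before any ethics or authority submission and may terminate if the approved proposal is substantially altered. Section 20 requires mutual written consent. No new measurement is needed, because Table 1 schedules BCVA, OCT and colour fundus photographs at all 7 visits.

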**(4) Study Design**

single center, prospective, interventional, one arm, pilot study

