## **(7) Number of centers & patients, inclusion/exclusion criteria**

-25 patients, 1 center

- Inclusion criteria

- Patients (Male & female) > 40 years of age

- Type 2
- Best corrected visual acuity > 20/200 (Snellen equivalent using Early Treatment Diabetic Retinopathy Study chart)
- Central retinal thickness of > 300 um on optical coherence tomography
- Nonproliferative diabetic retinopathy (NPDR) with diabetic macular edema

- Exclusion criteria

- PDR – NVE & NVD
  - Early PDR – New vessels ; and criteria not met for high-risk PDR
  - High risk PDR – New vessels on or within one disc diameter of the optic disc (neovascularization of the disc) > standard photograph 10A with or without vitreous or preretinal hemorrhage ; or vitreous and/or preretinal hemorrhage accompanied by new vessels, either NVD < standard photograph 10A or new vessels elsewhere (NVE) > 1/4 disc area
- Vitreous hemorrhage
- Prior intraocular operation history.
  - Pars Plana Vitrectomy, RD surgery, recent (4 months) cataract Op, et al
- Prior any intravitreal injection history.
  - Lucentis, Eylea, Macugen, Avastin, Triamcinolone et al
- Prior pan retinal photocoagulation (PRP) or sector scatter photocoagulation was done.
- Uncontrolled hypertension.
- Uncontrolled glaucoma.

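### Perifoveal non-perfused area, tested across visits in a one-arm trial, rests on a discretionary FA frame at each visit and a threshold with no stated rule, and the plan does not mask the reader to visit.

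*Combined protocol and SAP*

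**What the plan says.** Section (4) describes a "single center, prospective, interventional, one arm, pilot study", and section (7) sets the size at "25 patients, 1 center". Section (10) lists "Perifoveal non-perfusion area in FAG" as item v of the secondary endpoints, with angiography at baseline, month 3 and month 6.

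Section (10) then describes the measurement:

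- **Frame.** One early FA image is taken from each of the three examinations, namely one "in which both the vascular arch and the non-perfused area were clearly visualized". No time window after dye injection is given.
- **Normalisation.** Contrast and sensitivity of each picture are equalised "by auto-adjustment of brightness and contrast".
- **Threshold.** After conversion to 8-bit, the image is processed "with the threshold set for optimal visualization of the non-perfused area". No numeric value or algorithm is named.
- **Safeguard.** "The same threshold was applied to all images of the same patient".

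The Statistical Analysis Plan in section (10) puts this endpoint through repeated measures ANOVA with Bonferroni correction at P<0.05. Section (11) names the Wilcoxon signed rank test for non-perfusion area and states no correction.

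Neither section says who reads the images, whether that person is masked to visit or image order, or whether there is a second reading. The only mention of blinding is in the drug-supply template of Annex 4, which does not concern image reading.

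**The concern.** The reported result is a within-patient change between visits. With no concurrent control, a reading habit that differs by visit cannot be subtracted out; it goes straight into the estimated change and its P-value.

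Two steps are open to such a habit. The first is frame choice, made separately at each visit and judged partly by how clearly the measured feature itself shows. The second is the threshold, for which no objective rule is stated. A reader who knows the visit and expects the drug to help could, without intending to, favour frames or a common threshold that widen the difference. The plan contains no step that prevents this. By contrast, microaneurysms are measured automatically with Retmarker on fundus photographs.

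**Working it through.** The documents contain no power calculation, SD or reader-error figure, so there is no stated number to reproduce. The check has two parts: which route stays open once the shared threshold is allowed for, and what an assumed shift would do to the test.

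**Inputs from the documents.** n = 25 (section (7)); three FA visits (section (10)); significance level 0.05 with Bonferroni correction (Statistical Analysis Plan).

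**Assumptions.** Two-sided testing. Three pairwise visit comparisons, so 0.05/3 = 0.0167 each. A paired t-test as a stand-in for one pairwise comparison. No true change. A systematic visit-linked reading shift δ, in units of the SD of the within-patient change. The values of δ are chosen for illustration.

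**Part 1: what the shared threshold cancels.** Let the measured area of a patient at visit j be A_j + c + b_j, where c is an additive offset from the common threshold and b_j a shift from frame choice at that visit. The change from baseline is (A_j − A_0) + (b_j − b_0). The offset c drops out; the frame term does not. A simulation of the paired test (20,000 runs, 25 patients, 5% level) agrees:

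| Reading error | Rejection rate, no true change |
|---|---|
| 0.3 SD offset common to all images of a patient | 4.9% |
| 0.3 SD shift at one visit only | 30.4% |
| Common 0.3 SD offset plus 0.3 SD frame shift | 30.4% |

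The cancellation requires the threshold error to be additive and equal across images. Section (10) adjusts brightness and contrast on each picture before thresholding, so one threshold value need not mean the same thing on each image. A common value chosen with all three images in view could also favour a larger difference. The threshold route is therefore reduced rather than closed, and the frame route is untouched.

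**Part 2: effect on the false-positive rate.** The statistic is t = mean change / (SD/√n). With shift δ it follows a noncentral t distribution with 24 df and noncentrality δ√25 = 5δ. The false-positive rate is P(|t| > t_crit). The critical mean change is t_crit/√25, which is 0.41 SD at 0.05 and 0.51 SD at 0.05/3.

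| Assumed δ (SD of change) | Noncentrality | At 0.05 | At 0.05/3 |
|---|---|---|---|
| 0 | 0 | 5.0% | 1.7% |
| 0.1 | 0.5 | 7.7% | 2.9% |
| 0.2 | 1.0 | 16.1% | 7.4% |
| 0.3 | 1.5 | 30.2% | 16.3% |

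The 0.05 column is closer to section (11), which states no correction; the 0.05/3 column is closer to the Statistical Analysis Plan in section (10). At δ = 0.3 the corrected rate is 16.3/1.67, or about 9.8 times its nominal level.

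**The case against.** The strongest reply is that the plan already constrains the reading. The frame must be early and must show two named features clearly. Contrast adjustment is automatic. One threshold per patient means it cannot be reset from visit to visit, and an additive error in it cancels. Nothing shows that choosing a clear frame would move the area in one direction by visit. The endpoint is secondary, in a 25-patient pilot, and the error rates would look the same for any bias in any paired endpoint.

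Most of this stands as a limit on the point. A reader might infer that the threshold is set by eye by someone who knows the visit. The documents do not support that as fact: they do not identify the reader, the reading order or the labels visible, nor whether the threshold is manual or computed. A reader might also infer that the threshold can be moved visit by visit; section (10) says otherwise. And the uncorrected rates alone would overstate the effect under the Bonferroni-corrected analysis, which is why both columns are shown.

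What remains is that no masking is required, no time window or threshold rule is given, and the shared threshold does nothing about frame choice.

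**Conclusion.** The point holds as a gap in protection. The plan leaves frame choice discretionary at each visit, gives no rule for the threshold and does not mask the reader to visit, in a design with no control to absorb a visit-linked shift. The single threshold per patient limits expectation bias without removing it.

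It does not show that bias occurred, in which direction it would run, or how large it would be. The calculated rates depend on the assumed shifts and, for the corrected column, on three comparisons; they show only how sensitive a 25-patient paired comparison is. The scope is one secondary endpoint: the automated microaneurysm measures are not touched by this argument. The change is worth making because it is cheap and closes a route that the analysis cannot correct afterwards.

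**What to change.** Add a masked reading step to section (10):

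1. A script, or an existing staff member other than the reader, strips date and visit labels from the FA frames of all three visits, shuffles them within patient and holds the key.
2. The same reader picks one frame per examination, sets the one patient threshold and locks the areas.
3. Only then are the areas linked to visits.

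The frames must stay grouped by coded examination so that one can be picked from each.

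Section (10) is written in the past tense and cites software dated 23/04/2018, so reading may already have been done. If it was unmasked, repeat it this way on the stored images. If it was masked, one sentence saying so settles the point.

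The cost is a small amount of file handling, or one re-read of up to 25 × 3 = 75 examinations, with no extra patient procedure and no additional reader. Masking will be imperfect, since reduced leakage on later images may hint at the visit. It also leaves the early frame and the optimal threshold undefined; stating a time window and a threshold rule alongside it would make the reading reproducible.
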